8.1.4. Diagnosis of Adverse Event

There should be an attempt to report a "diagnosis" of the adverse event, rather than the individual signs associated with the diagnosis. However, a diagnosis should be reported only if, in the investigator's judgment, it is relatively certain (i.e., definite or possible). Otherwise individual signs and symptoms should be reported as the adverse events.

8.1.5. Anticipated Outcome Related Adverse Events

Anticipated adverse events in this study may include:

- Skin reactions including: flare-up, irritation, infection, blistering, pruritis, dryness, temporary skin color changes, burns, prolonged edema or erythema, *Herpes simplex* virus reactivation, post-inflammatory hyperpigmentation (PIH), contact dermatitis, and scarring. If any antibiotic ointment will be required during the study it will be provided by the study investigator at no cost.
- Ocular conditions including: iritis, iris atrophy, uveitis, elevated IOP, photophobia, floaters

Any anticipated AE that occurs at any time during or after the use of the study device must be reported by the study investigator to Lumenis. If the anticipated AE, in the opinion of the Sponsor (Lumenis) or the study investigator, is likely to affect the safety of the subjects or the conduct of the study, the ethical committee will be notified of the effect within 10 working days after Lumenis first

QF-1044440 Rev. D	Global Clinical Study Report Template	GEN-0010523	Effective Date: July-2017

Revision: C State: Released ECO No: ca-00000172 Effective Date: 19-Sep-2019

receives notice of the event. If an adverse event occurs during the course of the study, the study investigator will continue following the subject until the adverse event is resolved, or up to 6 months following the last treatment, whichever comes first.

8.1.6. Unanticipated Adverse Device Effects

An unanticipated adverse device effect as defined by the Federal Regulations [21 CFR 812.3(s)] is "any serious adverse effect on health or safety or any life-threatening problem or death caused by, or associated with, a device, if that effect, problem, or death was not previously identified in nature, severity, or degree of incidence in the investigational plan or application (including a supplementary plan or application), or any other unanticipated serious problem associated with a device that relates to the rights, safety, or welfare of subjects." From a practical perspective, an unanticipated adverse device effect means a serious adverse event that is not listed in the device labeling, or the frequency or severity is greater than reported in the device labeling.

In the event of an unanticipated adverse event, the Investigator will immediately notify the contact person at Lumenis by telephone. If such an adverse event is being reported after normal working hours, the Investigator will leave a voice message at the telephone number below with accompanying report of the adverse event.

8.1.7. Serious Adverse Events (SAEs)

The term "serious" is not synonymous with "severe", the latter being used to describe the intensity of an event experienced by the subject. Any AE that does not meet any of the below criteria will be classified as non-serious. Any AE that meets one or more of the below criteria, will be classified as a serious adverse event (SAE).

An SAE is any event that satisfies one or more or the following:

- results in, or contributes to a death;
- is immediately life-threatening (injury or illness);
- results in hospitalization, or prolongs an existing hospitalization;
- results in permanent impairment of body structure or function, or in persistent or significant disability/incapacity;
- results in an injury that requires medical intervention to prevent permanent impairment of body structure or function;
- is a device malfunction or deterioration in the characteristics and/or performance of the device that results in death or serious deterioration in health;
- is a device malfunction or deterioration in the characteristics and/or performance of the device that, if it were to occur again, could result in death or serious deterioration in health;
- results in a congenital anomaly or birth defect;
- is any medically significant injury, event or experience that requires medical/surgical intervention to prevent one of the outcomes listed above;

QF-1044440 Rev. D Global Clinical Study Report Template GEN-0010523 Effective Date: July-20	,,,
---	-----

• results in end-organ toxicity, including hematological, renal, cardiovascular, hepatic, gastrointestinal, and central nervous system events.

8.2. Reporting

8.2.1. Adverse Events (AE) and Severe Adverse Events (SAE) Reporting

All serious adverse events, whether or not deemed expected or device-related, must be reported to the contact person at Lumenis within 24 hours by telephone (see below). A written report must follow within five (5) working days and is to include a full description of the event and sequence of events. The site personnel will directly contact the Lumenis Clinical Director ([contact], [name], [name]).

The AE source document must be completed for all adverse events and serious adverse events. AE and SAE data must then be promptly entered into the AE eCRF for review by the Sponsor and CRO.

In addition to reporting adverse events within the context of this clinical study, 21 CFR Part 803 Medical Device reporting requirements and any applicable local device reporting requirements will be followed.

8.2.2. Device Malfunctions/Medical Device Reporting

Each device failure will be assessed for possible reporting as a Medical Device Report (MDR), and a determination will be made in accordance with the Sponsor's standard operating procedure. MDRs will be reported in accordance with 21 CFR 803. For all device malfunctions, notify the contact person at Lumenis within 24 hours.

8.3. Risk/ Benefit Analysis

8.3.1.Risks

Skin erythema or edema is anticipated and should resolve spontaneously, generally within a few hours and more rarely within a few days. More rare complications include skin flare-up, irritation, infection, blistering, pruritis, dryness, temporary skin color changes, burns, prolonged edema or erythema, *Herpes simplex* reactivation, post-inflammatory hyperpigmentation (PIH) and scarring. These complications should all resolve within a few days, possibly with topical treatment such as anti-biotic, steroids, or anti-inflammatory creams or ointments.

Use of IPL without protecting the eyes at all times with fully occluding goggles may result in severe ocular complications, including: iris photo-ablation, pupillary defects, uveitis, photophobia, pain, posterior synechiae and iris trans-illumination defects.

8.3.2. Anticipated Benefits

For patients in the study arm, the anticipated benefit that may be observed in this study is the relief of signs and symptoms of DED, as measured by the tests and surveys required in this protocol. In addition, a previously proven benefit from IPL treatments, while not the objective of this study, is improvement in the appearance of the skin in the treated area.

Patients in the control arm may experience a smaller improvement of their signs and symptoms of DED, possibly due to a placebo effect.

9. Administrative Procedures

9.1. Investigator Selection

The investigator must be of good standing as an investigator and knowledgeable in relevant areas of clinical research to ensure adherence to the requirements of the protocol, including the protection of human subjects. Other site personnel must have appropriate research experience and infrastructure to ensure adherence to the protocol and enrollment of sufficient numbers of evaluable subjects. The curriculum vitae (CV) of the Investigator will be maintained in the Sponsor files as documentation of previous medical training, and federal databases will be searched to ensure that the investigator and/or the site are not prohibited from engaging in federally governed clinical research. The Principal Investigator will sign the signature page of this protocol, agreeing to comply with all applicable government regulations and the requirements of this study.

9.2. Institutional Review Board (IRB) Approval

This clinical study will be conducted according to all applicable regulations under 21 CFR Part 812, and 21 CFR Parts 50 and 56, and with local laws and regulations relevant to the use of medical devices.

An Institutional Review Board (IRB) will approve the clinical study protocol prior to study initiation. Approval will be indicated in writing with reference to the final protocol number and date. Details regarding the IRB's constitution including the names of its members, their qualifications and what function they perform on the board (e.g., chairman, specialist, lay-member) will be made available to enable Lumenis and the Investigator to conform to regulations governing research on experimental devices.

9.3. Case Report Forms/Data Collection

Error! Reference source not found. summarizes all forms and questionnaires required to be completed for all study subjects enrolled and treated in this study. An electronic data capture (EDC) system, *IBM Clinical Development,* will be utilized to capture this information. The *IBM Clinical Development* system is a cloud-based system which is compliant with 21 CFR Part 11.

Study worksheets (source documents) will be provided by the sponsor for each subject enrolled in the study. In order to facilitate data entry, the worksheets coincide with the data entry pages in

the EDC system. The appropriate worksheets will be completed by designated site personnel and initialed or signed where indicated at each examination. All worksheets will be completed in a legible manner in black/blue ink. Any corrections to the worksheets will be made by drawing a single line through the incorrect entry, recording the correct information, and initialing and dating the change.

Completed study worksheets shall be promptly entered into the EDC system by designated site staff. The study worksheets and data entered in the EDC system will be audited by the Study Monitor.

Study investigators are responsible for ensuring site staff completely and accurately records study data in the appropriate sections of the worksheets and eCRFs. All eCRFs must be signed by the Investigator in the EDC system.

The CRO will ensure completeness and data accuracy at each investigational site by comparing all study worksheets (source data) to data entered in the EDC system during periodic site visits. Recording errors will be addressed and rectified by designated site staff. Adherence to GCPs for proper recording of information as well as ensuring required corrections are made will also be addressed during these periodic visits.

All clinical data generated in the study will be submitted to Lumenis or designated CRO for quality assurance review and statistical analysis. Computerized data checks will be used to identify unusual data entries for verification prior to statistical analysis.

9.4. Required Documentation

[figure not shown]
Prior to starting the clinical study, the following documents must be submitted or returned to Lumenis:

- Signed Clinical Trial Acknowledgement (signature in Appendix I) for the protocol (signed acknowledgement may be sent via email with original copy to follow via mail – one signed copy should be retained by the Investigator for his/her files.
- Signed Clinical Evaluation Agreement
- Curriculum vitae of the Principal Investigator
- Signed Financial Disclosure Statement for each investigator
- IRB Assurance of Compliance form or equivalent
- Written approval from the IRB of both the protocol and informed consent form

9.5. Device Use/Accountability

The study site personnel will maintain records of the model and serial number of the device (if appropriate) used for each treatment during the conduct of the study on a Device Accountability Log. Receipt and disposition of the devices will also be maintained on the log. The device along with the associated delivery handpieces and accessories are to be maintained by the research Sponsor with

QF-1044440 Rev. D	Global Clinical Study Report Template	GEN-0010523	Effective Date: July-2017

reasonable care being taken by the Investigators and facility to prevent damage to, or unauthorized use of, the equipment. The device along with associated delivery handpieces and accessories are not to be used for other non-research subjects during the conduct of the evaluation.

9.6. Training Requirements

Both the Study Investigators and the Sponsor, prior to any independent use of the device, will agree upon the Investigators' training requirements. Prior to the study, the Sponsor will ensure that each investigator has received in depth training on the use of the device. Device and study related training will be documented on a Training Log.

9.7. Modification of Protocol

The protocol may be amended with the written agreement of the Sponsor and upon notification of and approval by the IRB. Investigators should review the contents of the amended protocol. Subsequent alterations should only be made in written conjunction with the Sponsor.

Medically significant amendments to the protocol (e.g., changes that increase the risk or the inconveniences for the patient, changes to the inclusion/exclusion criteria, etc.) must be approved by the IRB prior to implementation.

9.8. Data Retention/Archiving Data

The Investigator must keep the following documents in a secure place for at least 2 years after the last clearance of a marketing application or at least 2 years have elapsed since the formal discontinuation of clinical development of the investigational product.

- A signed copy of the final protocol and amendments.
- Copies of the subjects' study worksheets, clinical charts, all source data, any associated subject-related raw data or, where applicable, authorized copies of raw data.
- Clinical images or photographs stored on flash drives or similar electronic media.
- The subjects' signed Informed Consent forms.

9.9. Study Monitoring

Lumenis and the CRO will oversee the conduct and progress of the study and will be in regular communication with the study investigators and site staff. Study monitoring will be managed by the CRO. The study monitors will be involved in inspection and review of sites and records, to ensure continued compliance with the protocol, appropriate use of the investigational device, and adequacy of the investigators and the facilities to carry out the study.

The study will be monitored by the CRO using telephone calls, email correspondence and on-site visits. At a minimum, visits to each site will be conducted at the initiation of the study, at two interim points during the study, and at termination of the study.

QF-1044440 Rev. D	Global Clinical Study Report Template	GEN-0010523	Effective Date: July-2017

Revision: C State: Released ECO No: ca-00000172 Effective Date: 19-Sep-2019

9.10. Termination of Study

Lumenis reserves the right to discontinue the study at any time for administrative or other reasons. Written notice of study termination will be submitted to the investigator in advance of such termination. Termination of a specific site can occur because of (but is not limited to) inadequate data collection, low subject enrollment rate, achievement of the total enrollment, or non-compliance with the protocol or other clinical research requirements.

9.11. Reporting Requirements

The investigator must promptly report to Lumenis any withdrawal of IRB approval at the site. Additional reporting requirements include:

- Notify Lumenis' designee and to the IRB a report of any severe adverse device effect, whether
 anticipated or unanticipated, that occurs during the study as soon as possible, but in no event
 later than 10 working days after the investigator first learns of the effect. This report is to
 include a description of the effect, subsequent treatments, clinical outcomes, and outcome
 diagnoses. If the site personnel are not sure whether an event meets these criteria, they should
 call the contact person at the CRO or Lumenis.
- Notify Lumenis, the CRO, and the IRB immediately (within 24 hours) if an emergency situation arises in which the subsequent treatment, in the best interests of the subject, requires a deviation from the protocol. This should be followed with written confirmation that describes the emergency action and outcomes, to Lumenis, the CRO and the IRB within 5 working days.
- Report to the IRB and Lumenis, within 5 working days, the use of the study device without signed informed consent from the subject.
- Report adverse events in accordance with 21 CFR 803.
- Submit regular progress reports to the IRB, Lumenis or the CRO, as requested by the investigators or IRB.
- Submit a final report of the study to the IRB, the CRO and Lumenis within 3 months after termination or completion of the study.

10. References

Table 5. References

- [1] M. Lemp, L. Crews, A. Bron, G. Foulks and B. Sullivan, "Distribution of aqueous-deficient and evaporative dry eye in a clinic-based patient cohort," *Cornea*, vol. 27, pp. 1142-1147, 2008.
- [2] J. Nelson, J. Shimazaki, J. Benitez-del-Castillo, J. Craig, J. McCulley, S. Den and G. Foulks, "The international workshop on meibomian gland dysfunction: report of the definition and classification subcommittee," *Invest. Ophthalm. Vis. Sci.*, vol. 52, no. 4, pp. 1930-7, 2011.
- [3] G. Geerling, J. Tauber, C. Baudouin, E. Goto, Y. Matsumoto, T. O'Brien, M. Rolando, K. Tsubota and K. Nichols, "The international workshop on meibomian gland dysfunction: report of the subcommittee on management and treatment of meibomian gland dysfunction," *Invest. Ophthalmol. Vis. Sci.*, vol. 52, no. 4, pp. 2050-64, 2011.
- [4] J. Ding and D. Sullivan, "Aging and dry eye disease," *Exp. Gerontol.,* vol. 47, no. 7, pp. 483-90, 2012.

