8.1.1. Severity

Each adverse event should be assessed for its severity, or the intensity of an event experienced by the subject.

- **Mild:** Awareness of a sign or symptom that does not interfere with the subject's activity or is transient, resolved without treatment and has no sequelae.
- **Moderate:** May interfere with the subject's usual activity and require additional intervention and/or treatment, and may have additional sequelae.
- **Severe:** Significant discomfort to the subject and/or interferes with the subject's activity. Additional intervention and or treatment are necessary. Additional sequelae occur. Severe is used to describe the intensity of an event experienced by the subject.

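### Section 9.11 triggers the investigator's IRB report by *severe* rather than *serious* device effect, so an unanticipated serious effect not graded severe has no express event-triggered IRB report

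*Protocol*

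**What the plan says.** Protocol 9.11 lists what the investigator must report. Its first item requires notice to the sponsor's designee and "to the IRB a report of any severe adverse device effect", whether anticipated or unanticipated, no later than 10 working days after the investigator learns of it.

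Two definitions bear on that trigger:

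- 8.1.1 grades every adverse event as mild, moderate or severe, and adds: "Severe is used to describe the intensity of an event experienced by the subject".
- 8.1.7 states that *serious* and *severe* are not synonyms, "the latter being used to describe the intensity of an event experienced by the subject". It then lists the criteria for a serious event. One is a device malfunction or deterioration that, "if it were to occur again, could result in death or serious deterioration in health".

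The reporting sections then say:

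- 8.2.1 is headed "Adverse Events (AE) and Severe Adverse Events (SAE) Reporting", but its body concerns serious events. Each of these "must be reported to the contact person at Lumenis within 24 hours by telephone", with a written report within five working days.
- 8.1.6, on unanticipated adverse device effects, says: "In the event of an unanticipated adverse event, the Investigator will immediately notify the contact person at Lumenis by telephone".

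**The concern.** The protocol separates intensity from seriousness and then ties its device-effect report to the IRB to intensity. The two classes differ. A malfunction that hurt nobody but could cause serious harm next time is serious under 8.1.7, although the subject may have felt little or nothing. A site that follows 9.11 literally would tell the sponsor and need not tell the IRB.

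What is at stake is IRB oversight of the trial's most important safety signals. Unanticipated serious adverse events are a named safety endpoint (Protocol 3.5.5, SAP 2.5), and Protocol 8.3.1 acknowledges severe ocular complications if the eyes are not protected. The IRB should hear of such events according to their consequence.

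**Working it through.** No arithmetic applies. The check is to find every route by which a device effect could reach the IRB and see what triggers it.

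| Protocol section | Trigger | Recipient named | Depends on intensity? |
|---|---|---|---|
| 5.3.3 | Any SAE, at the follow-up visit | Sponsor, 24 hours | No |
| 8.1.5 | Anticipated AE that the sponsor or investigator thinks likely to affect subject safety or study conduct | Ethics committee, 10 working days | No, but depends on judgement |
| 8.1.6 | Unanticipated event | Sponsor, immediately | No |
| 8.2.1 | Any SAE, expected or not, related or not | Sponsor, 24 hours, then in writing | No |
| 8.2.2 | Device malfunction | Sponsor, 24 hours | No |
| 9.11, first item | *Severe* device effect, anticipated or not | Sponsor's designee and IRB, 10 working days | **Yes** |
| 9.11, other IRB items | Emergency deviation, use without consent, progress reports on request, final report | IRB among the recipients | No; none is triggered by seriousness |
| 9.2 | General commitment to 21 CFR Parts 812, 50 and 56 | No event-reporting step given | Not applicable |

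Now follow a serious device effect that is not graded severe.

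1. **Unanticipated.** 8.1.6 defines an unanticipated adverse device effect as serious, so each one is a serious event under 8.2.1 as well. Both sections send it to the sponsor; 5.3.3 and 8.2.2, where they apply, do the same. 8.1.5 does not apply, because it covers anticipated events. The 9.11 item does not apply, because the effect is not severe. No express event-triggered report to the IRB remains.

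2. **Anticipated.** The 9.11 item again does not apply. 8.1.5 provides for notice to the ethics committee, but only if someone judges the event likely to affect safety or conduct. The protocol never equates that committee with the IRB, though the IRB is the only approving body it describes (9.2).

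3. **Is the class empty?** No. The malfunction criterion in 8.1.7 looks to what a recurrence could do, not to what the subject experienced. An event that meets it need not be graded severe. If it is not listed in the device labeling, the practical definition in 8.1.6 makes it unanticipated, and it falls under case 1.

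**The case against.** The strongest reply is that this is a drafting slip that nobody would follow. Under its mislabelled heading the body of 8.2.1 speaks of serious events, and the abbreviation list expands SAE as serious. The document therefore already writes *severe* where it means *serious*, and 9.11 can be read the same way. It probably is a slip. But in 8.2.1 the body text corrects the heading, whereas in 9.11 *severe* is the operative word and nothing beside it corrects it.

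Safeguards exist. Every SAE reaches the sponsor within 24 hours whatever its intensity. 9.11 tells sites that are unsure whether an event qualifies to call the CRO or the sponsor. 9.2 binds the study to the device regulations. These reduce the risk, but they do not create an IRB step: the advice to call does not help a site that is confident of a moderate grade, and 9.2 sets out no action for site staff. What those regulations require cannot be checked from these documents, and this point does not rely on their content.

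Three stronger readings are tempting and are not supported:

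- *Serious effects below severe have no written route to the IRB at all.* This is too broad. 8.1.5 gives anticipated events a conditional ethics-committee route with no intensity condition, and progress and final reports also go to the IRB.
- *Two of the three intensity grades escape the rule.* This is not a measure of size. Most criteria in 8.1.7 hardly fit *mild*. An event needing intervention to prevent permanent impairment may well be graded severe, since 8.1.1 describes severe events as needing additional intervention.
- *A moderate ocular inflammation would be an unreported unanticipated effect.* 8.1.5 lists iritis and uveitis as anticipated, so without a further assumption about severity or frequency the conditional route applies.

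**Conclusion.** The point holds in a narrow form. Section 9.11 uses a term that 8.1.7 itself distinguishes from the one needed. Read literally, it leaves an unanticipated serious device effect not graded severe without an express event-triggered report to the IRB. An anticipated one has only the judgement-based route in 8.1.5.

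The realistic class is serious effects graded moderate, plus malfunctions whose harm is only potential. Its frequency cannot be given from the documents, and they show no such event. The conclusion assumes that sites apply 9.11 as worded, and that the ethics committee in 8.1.5 is the IRB; if it is not, the gap for anticipated effects is wider.

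This is an internal wording inconsistency in a safety-reporting rule. It does not touch the endpoints, sample size, power, type I error or the SAP's safety analysis. Severity is minor, but the wording is worth correcting because the rule is operative and the change is almost free.

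**What to change.** 1. In 9.11, replace *severe adverse device effect* with *serious adverse device effect, including any unanticipated adverse device effect (8.1.6), irrespective of intensity*. If severe but non-serious device effects are still meant to go to the IRB, say so separately.
2. Correct the heading of 8.2.1 so that SAE is expanded as *Serious Adverse Events*.
3. In 8.1.6, add a cross-reference to 9.11 so that the IRB step is visible where the sponsor call is described.
4. Reconcile 8.1.5 with 9.11: state whether its ethics committee is the IRB, and how its conditional notice relates to the 9.11 report.
5. Check events already recorded against the corrected trigger, and report to the IRB any that were missed.

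The cost is a few lines in a protocol amendment and a short look-back over the adverse event log. The SAP needs no change.
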